3.2. Study Schematic

The study schematic is provided in [Figure 1](#).

Figure 1. Study Schematic

3.3. Blinding

Treatment with enzalutamide monotherapy will be open label.

Treatment with enzalutamide and placebo will be double-blind in combination with open-label leuprolide.

All patients, study site personnel (including investigators), and sponsor staff and its representatives will be blinded to enzalutamide or placebo treatment assignment when administered in combination with leuprolide. The blinded control for enzalutamide will be placebo capsules identical in appearance to the enzalutamide capsules.

The procedure for breaking the blind in an emergency is provided in [Section 8.2.2](#).

3.4. Duration of Study

The duration of this study until the final analysis will be approximately 90 months (time of first randomization until a total of at least 197 MFS events are observed in all 3 arms). One interim analysis and a final analysis of overall survival will be performed. The interim analysis for OS will be performed at the time of the final analysis of the MFS primary endpoint. Long-term follow-up data (survival status, skeletal-related events and new prostate cancer therapies) will be collected every 12 weeks until the final analysis of OS.

Because skeletal events are expected to occur after radiographic progression the analysis of time to first symptomatic skeletal event will be performed with the final overall survival analysis.

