10.7. Determination of Sample Size

The following assumptions were used in determining the sample size for this study:

- Overall type I error rate: 0.05;
- Patient accrual rate: Utilizing an adaptive enrollment rate, the following rate has been modified into two arms to fit into EAST v6.4 software from Cytel.

Period #	Starting at Time	Accrual Rate
1	0	6
2	12	17.3
3	24	16.6
4	27	19.3
5	30	28.3
6	34	22
7	38	30
8	42	33.3
9	44	28.7
10	48	33.3

- Randomization: 1:1:1;
- Median MFS for the control group: 55 months.

An observed 142 MFS events in the 2 blinded treatment groups will provide approximately 90% power to detect a target hazard ratio of 0.58 using a 2-sided log-rank test with a 0.05 level of significance. This target hazard ratio corresponds to a difference of approximately 40 months in median MFS assuming an exponential distribution in the duration of MFS and a constant hazard rate for each group. For the key secondary hypothesis of MFS between the monotherapy arm, the target effect size, and expected number of MFS events will be the same as the primary hypothesis in the combination arm. As the 2-sided alpha level will be 0.03 for the monotherapy arm comparison, the power for this analysis will be 86% with 142 MFS events observed. At the time of the final analysis, at least 197 MFS events total are required for the 3 treatment groups. An enrollment of approximately 1050 patients (350 in each group) is required to achieve the targeted total of 197 MFS events allowing for a 5% loss to follow-up, as outlined in the Statistical Analysis Plan.

An actual enrollment of 1068 patients will also allow for an assessment for the key secondary endpoint of OS, assuming a 5-year OS rate of 80% for the control arm and hazard ratio of 0.67.

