10.8. Interim Analysis

There will be no interim analysis for the primary endpoint (MFS). The interim and final analyses for the key secondary endpoint OS will be performed after the target number of events have occurred in the 3 treatment arms. A maximum of 2 distinct analysis cut-offs are planned according to the approximate number of events as described below:

- Final MFS and OS Interim: when at least 197 MFS events have occurred as assessed by the independent central radiology review have occurred in the 3 treatment groups;
- Final OS: when 271 deaths have occurred in the 3 treatment groups.

Table 14 shows the efficacy boundary associated with the final analysis of the primary endpoint of MFS between enzalutamide plus leuprolide and placebo plus leuprolide, according to independent central radiology review.

Table 14. MFS Based on Independent Review (2 blinded treatment arms) - Efficacy Boundary

Analysis	Analysis Cut-off Trigger	Number of MFS Events (2 blinded arms) ^a	Fraction of Required MFS Events	p-value (z-value) for Efficacy
Final MFS	197 MFS events in 3 arms	142	100%	≤ 0.05 (-1.9600)

a. Number of events expected for MFS in blinded treatment arms assuming a hazard ratio of 0.58.

Table 15 shows the analysis triggers for OS as well the associated Haybittle-Peto efficacy boundaries. The significance level for the analyses of this key secondary endpoint is determined by the gatekeeping procedure.

Table 15. OS (2 blinded treatment arms) - Efficacy Boundaries

Analysis	Analysis Cut-off Trigger	Number of OS Events (2 blinded arms)^a	Fraction of Required OS Events	p-value (z-value) for Efficacy^b
IA OS	197 MFS events in 3 arms	82	43%	≤0.0001 (-3.89059)
Final OS	271 OS events in 3 arms	191	100%	≤0.04999 (-1.96001)

- a. Number of events expected for OS in blinded treatment arms assuming a hazard ratio of 0.67.
b. The p-values and z-values noted for OS are those associated with the scenario where all the key secondary endpoints for the blinded treatment arms and the monotherapy arm are statistically significant ($\alpha=0.05$).

Safety data will be summarized as described in [Section 10.5](#). The timing and details of the E-DMC review are described in [Section 11](#). The Statistical Analysis Plan (SAP) will describe the planned interim analysis in greater detail.

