5. GENERAL METHODOLOGY AND CONVENTIONS

5.1. Hypotheses and Decision Rules

5.1.1. Hypotheses and Sample Size Determination

The study is designed to test the following primary hypothesis:

$$H_{0l}: \frac{\lambda_{TrtA}}{\lambda_{TrtC}} = 1$$
, versus $H_{al}: \frac{\lambda_{TrtA}}{\lambda_{TrtC}} \neq 1$, where

Trt A: Enzalutamide plus leuprolide;

Trt C: Placebo plus leuprolide.

The sample size and event-driven readout was chosen to adequately power the testing of the primary endpoint of MFS.

The comparison of MFS for enzalutamide monotherapy versus placebo in combination with leuprolide is a key secondary endpoint.

The following assumptions were used in determining the sample size calculation for the MFS endpoint:

- Overall 2-sided Type I error rate: 0.05
- Patient accrual rate: An adaptive enrollment rate has been modified into 2 arms to fit into EAST v6.4 software from Cytel
- Randomization: 1:1:1
- Median MFS for the control group: 55 months

An observed 142 MFS events in the 2 blinded treatment groups will provide approximately 90% power to detect a target hazard ratio of 0.58 using a 2-sided log-rank test with a 0.05 level of significance. This target hazard ratio corresponds to a difference of approximately 40 months in median MFS assuming an exponential distribution for MFS and a constant hazard rate for each group. For the key secondary hypothesis of MFS for the monotherapy arm, the target effect size, and expected number of MFS events will be the same as the primary hypothesis in the combination arm. As a 2-sided alpha of 0.03 will be utilized for the monotherapy comparison, the power for this analysis will be 86% with 142 MFS events observed. At the time of the final analysis, at least 197 MFS events total are expected for the 3 treatment groups. The study will require approximately 1050 patients (350 in each group) to achieve the 197 MFS events across the 3 treatment arms. This sample

size calculation accounts for a 5% loss to follow-up by the end of 4 years for all 3 treatment groups.

An actual enrollment of 1068 patients will also allow for an assessment for the key secondary endpoint of OS.

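### Does it matter that the stated planning inputs reproduce neither the 90 months to 197 MFS events nor the 82 interim deaths?

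*Protocol*

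**What the plan says.** Protocol 3.4 puts the study's duration up to the final MFS analysis at "approximately 90 months (time of first randomization until a total of at least 197 MFS events are observed in all 3 arms"). It ties the first look at survival to the same date: "The interim analysis for OS will be performed at the time of the final analysis of the MFS primary endpoint".

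The planning inputs are in Protocol 10.7 and SAP 5.1.1:

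- MFS is exponential, with a control median of 55 months and a hazard ratio of 0.58 for both enzalutamide comparisons.
- Protocol 10.7 says: "An enrollment of approximately 1050 patients (350 in each group) is required to achieve the targeted total of 197 MFS events". SAP 5.1.1 says: "The study will require approximately 1050 patients (350 in each group) to achieve the 197 MFS events across the 3 treatment arms".
- On loss, the SAP's "size calculation accounts for a 5% loss to follow-up by the end of 4 years for all 3 treatment groups".
- A ten-period accrual table is introduced in Protocol 10.7 with "the following rate has been modified into two arms to fit into EAST v6.4 software from Cytel". It gives no units.
- For survival, Protocol 10.7 gives only "assuming a 5-year OS rate of 80% for the control arm and hazard ratio of 0.67". It names no survival distribution.

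Protocol Table 15 and SAP Table 3 list 82 deaths in the two blinded arms (43% of 191) at the 197-event trigger. The footnote describes this as "Number of events expected for OS in blinded treatment arms assuming a hazard ratio of 0.67".

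**The concern.** The inputs are complete enough to compute when 197 events should occur, and the answer is 32 to 40 months earlier than the 90 months stated. The death count attached to the same trigger does not come out either, if survival hazards are constant. When two forecasts fail to follow from the assumptions printed beside them, a reader has to ask whether the assumptions, the event targets or the power figures are wrong as well, and whether the OS boundary was computed at a wrong information fraction. If so, the primary result and the remaining OS test would both be affected. The statement that 1050 men are needed for 197 events adds to the doubt, because on these inputs 1050 men yield about twice that number by month 90.

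**Working it through.** **1. The figures that drive the tests.** With the usual log-rank approximation, power = Φ(|ln HR|·√D/2 − z).

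- MFS, D = 142, HR 0.58: 0.5447 × 11.916/2 = 3.246. Subtracting 1.960 gives power 90.1%. Subtracting 2.170 (alpha 0.03) gives 85.9%. The plan says about 90% and 86%.
- Median difference: 55/0.58 − 55 = 39.8 months. The plan says about 40.
- OS, D = 191, HR 0.67: 79.0%, 72.5% and 67.0% at alpha 0.05, 0.03 and 0.02. The plan says 79.0%, 72.3% and 67.0%.

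These agree with the plan, to within 0.2 points.

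**2. Time of the 197th event.** Monthly hazards:

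- control MFS: ln2/55 = 0.01260
- each enzalutamide arm: 0.58 × 0.01260 = 0.00731
- loss: −ln(0.95)/48 = 0.00107

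For an arm with event hazard λ, loss hazard δ and k = λ + δ, a period accruing a men per month from s to e contributes, by time T,

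a·(λ/k)·{(e − s) − [exp(−k(T − e)) − exp(−k(T − s))]/k}.

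Assumption: the table is in months and patients per month.

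- Two-arm reading: 588.5 men have entered by month 38, and (700 − 588.5)/30 = 3.7, so entry ends at month 41.7.
- All-arm reading: 889.9 men have entered by month 48, and (1050 − 889.9)/33.3 = 4.8, so entry ends at month 52.8.

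| | Two-arm rates | All-arm rates |
|---|---|---|
| Month of 197th event | 50.2 | 57.6 |
| Events then: control / each enzalutamide arm | 87.8 / 54.6 | 87.5 / 54.8 |
| Blinded-arm events then | 142.4 | 142.2 |
| Three-arm events at month 90 | 438 | 401 |

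The model returns the plan's own pairing of 142 with 197, so the event split is sound and only the calendar date differs.

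**3. Could the shape of accrual explain it?** If all 1050 men entered at once, 197 events would take 23.4 months. Entry of every man at month 52.8 would therefore still give 197 events by month 76.2. The accrual shape does not close the gap.

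**4. Interim deaths.** Add the assumption of constant OS hazards: −ln(0.80)/60 = 0.00372 for control and 0.67 × 0.00372 = 0.00249 for enzalutamide, with 1068/3 = 356 men per arm. Expected blinded-arm deaths at month 50.2 or 57.6 are 49 to 50, and 50/191 = 26%. The plan has 82/191 = 43%.

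This result depends on the assumed distribution. A Weibull survival curve that keeps 80% at 5 years and HR 0.67 gives 82 deaths at the computed cut-off with a shape of about 0.41 to 0.43. That is a heavily front-loaded hazard and perhaps unlikely here, but nothing stated rules it out.

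**5. What depends on either forecast.**

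- *Cut-offs.* Protocol 10.7 and 10.8 and SAP 5.1.2 trigger the analyses at 197 MFS events and 271 deaths, not at a date.
- *Interim boundary.* It is a fixed p-value of 0.0001 whatever the death count.
- *Final OS level.* The interim spends 0.0001. For a total of 0.05, the final nominal level must lie between 0.05 − 0.0001 = 0.0499 and 0.05, whatever the information fraction. If the stated 0.04999 were used at any fraction, the total could not exceed 0.0001 + 0.04999 = 0.05009.
- *Timing.* Protocol 3.1 and 18.1 report the primary analysis as done. Protocol 18.9 and SAP 5.1.2 already use its results to set the OS level at 0.05.

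**The case for a change.** The case for correcting the record is a fair one. The gap is large: about twice the trigger count by the stated date. Single-input explanations do not work either. Month 90 would need a control median of about 130 to 146 months, or about 34% loss per year. Censoring at new antineoplastic therapy, at radiation and after missed scans (SAP 6.1.1.1) does delay counted events, but alone it would have to act that strongly. Both current documents still carry the figures, the final OS analysis lies ahead, and a note on the basis would be a matter of wording.

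What stands is that the basis of the 90 months and of the 82 deaths, the units and arm coverage of the accrual table, and the OS distribution are not stated.

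What does not stand is the step from there to an error:

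- Protocol 3.4 does not say its figure was computed from 10.7. The 197-event target came with protocol amendment #4, and SAP Table 1, under the same amendment, gives 1068 as the actual enrollment. The 90 months may therefore be a projection made during the trial.
- Joint departures from the inputs come close to month 90. A control median of 90 months with HR 0.30 in both enzalutamide arms gives month 81 or 88. A median of 80 months, HR 0.40 and 10% loss per year gives month 79 or 87.
- The OS half rests on an added constant-hazard assumption.
- Saying that 1050 men are needed is loose wording. SAP Table 1 shows larger event targets before 197 (336 across the three arms immediately before), and Protocol 10.7 says enrollment also serves OS.
- Replacing 90 by 50 or 58 would put one unverified forecast in place of another. An amendment also has to go to ethics committees (Protocol 13.1), with about 200 centers planned.

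**Conclusion.** No change follows: this is missing detail about two forecasts, and correcting them would gain nothing. On the stated inputs, with the accrual table read as months and patients per month, 197 MFS events are expected at about month 50 (two-arm rates) or 58 (all-arm rates), not 90. With constant OS hazards, about 50 blinded-arm deaths (26%) are expected at that cut-off, not 82 (43%). Neither forecast enters a test, a trigger or a power figure. The event targets and powers reproduce, and the OS boundary is insensitive to the interim fraction to within 0.0001. The analyses that the forecasts describe are finished, so analysts will use the observed dates and death counts. If the documents are reopened for another reason, labelling both numbers as projections would be a courtesy to readers, but it would alter no result.

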3.5. Discussion of Study Design, Including Choice of Control Group

This study is designed to test whether enzalutamide plus leuprolide treatment or enzalutamide monotherapy can prolong MFS compared with placebo plus leuprolide treatment in men with biochemical recurrence of prostate cancer after primary therapy who are at high risk of morbidity and mortality. Prolongation of MFS is likely to delay or prevent prostate cancer symptoms and delay the need for subsequent therapies to treat prostate cancer (including cytotoxic chemotherapy).

The study population will be a subset of men with rising PSA following primary therapy that is at high risk for developing metastases, castration-resistant disease, and who will ultimately die as result of prostate cancer. High-risk prostate cancer is defined in this study as biochemical recurrence with a PSA doubling time ≤ 9 months and screening PSA by the central laboratory of ≥ 1 ng/mL for patients who had prior radical prostatectomy (with or without radiotherapy) and at least 2 ng/mL above the nadir for patients who had prior primary radiotherapy only. In theory, men who have rising PSA following definitive therapy have either occult metastatic disease or local progression, and it is likely that the great majority of these men have occult metastatic disease.^{[4],[15]} Enzalutamide is hypothesized to be effective in this setting of minimal tumor burden and disease that is not yet castration resistant based on an understanding of the mechanism of action of enzalutamide and data obtained in patients with hormone-naïve prostate cancer treated with enzalutamide monotherapy.^[16]

A key feature of the study design is to treat patients for a prespecified interval (36 weeks) and then to suspend treatment based on response as indicated by undetectable PSA (< 0.2 ng/mL), thus potentially averting the adverse effects associated with long-term continuous androgen deprivation therapy. Study drug treatment may be reinitiated if PSA rises to ≥ 2.0 ng/mL for patients who had prior radical prostatectomy or ≥ 5.0 ng/mL for patients who had prior radiation therapy. For patients whose PSA values are detectable at 36 weeks, assigned study drug treatment will continue. Only 1 such study drug treatment suspension is permitted during this study.

The control group is placebo with androgen deprivation therapy using leuprolide. Androgen deprivation therapy is appropriate in this disease setting as it is commonly used when a decision is made to treat patients with high-risk nonmetastatic disease with biochemical recurrence following definitive therapy.

4. SELECTION OF STUDY POPULATION

The specific eligibility criteria for selection of patients are provided in [Section 4.1](#) and [Section 4.2](#). The sponsor will not grant any eligibility waivers.

4.1. Inclusion Criteria

Each patient eligible to participate in this study must meet all of the following criteria:

1. Age 18 years or older and willing and able to provide informed consent.

2. Histologically or cytologically confirmed adenocarcinoma of the prostate at initial biopsy, without neuroendocrine differentiation, signet cell, or small cell features.
3. Prostate cancer initially treated by radical prostatectomy or radiotherapy (including brachytherapy) or both, with curative intent. Prostate cryoablation is not considered definitive therapy for this study, but its prior use is not exclusionary.
4. PSA doubling time ≤ 9 months as calculated by the sponsor.^[17]
5. Screening PSA by the central laboratory ≥ 1 ng/mL for patients who had radical prostatectomy (with or without radiotherapy) as primary treatment for prostate cancer and at least 2 ng/mL above the nadir for patients who had radiotherapy only as primary treatment for prostate cancer.
6. Serum testosterone ≥ 150 ng/dL (5.2 nmol/L) at screening.
7. Eastern Cooperative Oncology Group (ECOG) performance status of 0 or 1 at screening.
8. Estimated life expectancy of ≥ 12 months.
9. Able to swallow the study drug and comply with study requirements.
10. Throughout the study, the patient and his female partner who is of childbearing potential must use 2 acceptable methods of birth control (1 of which must include a condom as a barrier method of contraception) from screening through 3 months after the last dose of study drug or per local guidelines where these require additional description of contraceptive methods. Two acceptable methods of birth control thus include the following:

Condom (barrier method is required);

- AND

One of the following is required:

- Established and ongoing use of oral, injected, or implanted hormonal method of contraception by the female partner;
- Placement of an intrauterine device or intrauterine system by the female partner;
- Additional barrier method including contraceptive sponge and occlusive cap (diaphragm or cervical/vault caps) with spermicidal foam/gel/film/cream/suppository by the female partner;

- Tubal ligation in the female partner performed at least 6 months before screening;
 - Vasectomy or other procedure resulting in infertility (eg, bilateral orchiectomy), performed at least 6 months before screening.
11. Throughout the study, the patient must use a condom if having sex with a pregnant woman.
 12. Must agree not to donate sperm from first dose of study drug through 3 months after the last dose of study drug.

4.2. Exclusion Criteria

Each patient eligible to participate in this study must NOT meet any of the following exclusion criteria:

1. Prior or present evidence of distant metastatic disease as assessed by computed tomography (CT) or magnetic resonance imaging (MRI) or chest x-ray for soft tissue disease and whole-body radionuclide bone scan for bone disease. Patients with soft tissue pelvic disease may be eligible if the short axis of the largest lymph node is < 20 mm for lymph nodes below aortic bifurcation. If the screening bone scan shows a lesion suggestive of metastatic disease, the patient will be eligible only if a second imaging modality (plain film, CT, or MRI) does not show bone metastasis. If the imaging results are equivocal or consistent with metastasis by central radiology review, the patient is not eligible for enrollment. Positron-emission tomography (PET) is not an evaluable imaging modality for this study.
2. Prior hormonal therapy. Neoadjuvant/adjuvant therapy to treat prostate cancer ≤ 36 months in duration and ≥ 9 months before randomization, or a single dose or a short course (≤ 6 months) of hormonal therapy given for rising PSA ≥ 9 months before randomization is allowed.
3. Prior cytotoxic chemotherapy, aminoglutethimide, ketoconazole, abiraterone acetate, or enzalutamide for prostate cancer.
4. Prior systemic biologic therapy, including immunotherapy, for prostate cancer.
5. Major surgery within 4 weeks before randomization date.
6. Treatment with 5- α reductase inhibitors (finasteride, dutasteride) within 4 weeks of randomization.
7. For patients who had a prior prostatectomy, a suitable candidate for salvage radiotherapy as determined by the investigator in consideration of appropriate guidelines (eg, American Society for Radiation Oncology/American Urological Association [ASTRO/AUA]; European Association of Urology [EAU]).

8. Participation in a clinical study of an investigational agent that inhibits the androgen receptor or androgen synthesis (eg, TAK-700, ARN-509, ODM-201); patients who received placebo are allowed.
9. Use of any other investigational agent within 4 weeks before randomization date.
10. Known or suspected brain metastasis or active leptomeningeal disease.
11. History of another invasive cancer within 3 years before screening, with the exception of fully treated cancers with a remote probability of recurrence. The medical monitor and investigator must agree that the possibility of recurrence is remote.
12. Absolute neutrophil count $<1500/\mu\text{L}$, platelet count $<100,000/\mu\text{L}$, or hemoglobin $<10\text{ g/dL}$ (6.2 mmol/L) at screening. NOTE: May not have received any growth factors or blood transfusions within 7 days before the hematology values obtained at screening.
13. Total bilirubin (TBili) ≥ 1.5 -times the upper limit of normal (except patients with documented Gilbert's disease), or alanine aminotransferase (ALT) or aspartate aminotransferase (AST) ≥ 2.5 -times the upper limit of normal at screening.
14. Creatinine $>2\text{ mg/dL}$ ($177\text{ }\mu\text{mol/L}$) at screening.
15. Albumin $<3.0\text{ g/dL}$ (30 g/L) at screening.
16. History of seizure or any condition that may predispose to seizure (eg, prior cortical stroke or significant brain trauma). History of loss of consciousness (unless of cardiac origin) or transient ischemic attack within 12 months before randomization.
17. Clinically significant cardiovascular disease including the following:
 - Myocardial infarction within 6 months before screening;
 - Unstable angina within 3 months before screening;
 - New York Heart Association class III or IV congestive heart failure or a history of New York Heart Association class III or IV congestive heart failure unless a screening echocardiogram or multigated acquisition scan performed within 3 months before the randomization date demonstrates a left ventricular ejection fraction $\geq 45\%$;
 - History of clinically significant ventricular arrhythmias (eg, sustained ventricular tachycardia, ventricular fibrillation, torsades de pointes);
 - History of Mobitz II second-degree or third-degree heart block without a permanent pacemaker in place;

- Hypotension as indicated by systolic blood pressure <86 mm Hg at screening;
- Bradycardia as indicated by a heart rate of ≤ 45 beats per minute on the screening electrocardiogram (ECG);
- Uncontrolled hypertension as indicated by a minimum of 2 consecutive blood pressure measurements showing systolic blood pressure >170 mm Hg or diastolic blood pressure >105 mm Hg at screening.

18. Gastrointestinal disorder affecting absorption.
19. Hypersensitivity reaction to enzalutamide or any of the capsule components, including Labrasol, butylated hydroxyanisole, and butylated hydroxytoluene.
20. Contraindication to the use of leuprolide, such as a previous hypersensitivity reaction to an LHRH analogue or any of the excipients in the leuprolide injection.
21. Ongoing drug or alcohol abuse as per investigator judgment.
22. Any concurrent disease, infection, or comorbid condition that interferes with the ability of the patient to participate in the study, which places the patient at undue risk, or complicates the interpretation of data, in the opinion of the investigator or medical monitor.

